4.2. Patient Information Sheet

Informed consent will be obtained from all prospective study participants before any research procedures are initiated. Prior to this, the Investigator must fully inform a patient about all aspects of clinical research, including its purposes, study procedures, expected risks and benefits of participation, and voluntariness of participation.

The patient must be provided with written information about the study (Information Sheet), approved by the Ethics Committee. The patient's information sheet will contain all information about the planned clinical trial, as well as the terms of confidentiality and the use of the patient's data. The rights, safety, and well-being of the participants will take priority and prevail over the interests of science and society. If necessary, information about the procedure for obtaining informed consent from patients/volunteers can be submitted to the Ethics Committee.

Prior to the patient's participation in the clinical trial, two (2) copies of the Informed Consent Form with the patient's name must be signed and personally dated by the patient or the patient's legal representative, or by a person who conducted the informed consent discussion. One copy of signed and dated written Informed Consent will be provided to the patient, and the other will be kept by the Investigator.

When the patient's condition does not allow him/her to express his/her will and there is no legal representative and the need for treatment is urgent, the question of medical intervention in the interest of the patient and his/her inclusion in the study is resolved by a council of physicians, and if it is not possible – by his/her attending (duty) physician with following notification of the Principal Investigator, officials of the medical institution and the legal representative.

The Patient Information Sheet and Informed Consent Form must be reviewed and approved by the Ethics Committee. The final version of the Study Protocol, Individual Patient Registration Form, information for the patient, and Informed Consent Form must be approved by the Russian Ministry of Health and the Local Ethics Committee (if any) at the Research Center.

All subsequent amendments to the above-mentioned documents will also be submitted for approval to these institutions. In addition, these same institutions will be informed about all adverse events associated or possibly related to the use of the study drug.

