8. DESIGN AND PLAN OF RESEARCH ACTIVITIES

The current trial is a multicenter, open-label, randomized, parallel-group, phase III b non-inferiority trial to compare the efficacy and safety of the trial drug.

The trial will include 336 patients with ischemic stroke. The patients will be monitored for 90 days: 1-2 days in the Neurological Intensive Care Unit and the Department of Neurology in the remaining days before discharge (on average 14 days), with an outpatient visit on the 90th day.

Start of research, initiation of centers: «_____» 20___

Enrollment of patients: «_____» 20___

Result processing and reporting: «_____» 20___

The enrollment period may be extended to total patient enrollment if a research center fails to enroll the planned number of patients. The end date of the trial is considered to be the end date of the trial in all patients involved.

In each research center, the subject of the trial is assigned a serial number that corresponds to the sequence of patient inclusion in the trial. The serial number is reflected in the Case Report Form (CRF). The list of patient's identification is stored in the trial file. Patients are included in the trial only after signing the Informed Consent Form.

Before the trial, all patients will undergo the following procedures: collection of thorough medical history, measurement of vital signs, physical examination, assessment of neurological status, CT/MRI scans of the brain, duplex scanning, and angiography of the brain vessels (if necessary), ECG, blood and urine samples for laboratory tests:

***complete blood count:** hemoglobin, red blood cells, hematocrit, leukocyte formula: neutrophils, eosinophils, basophils, monocytes, lymphocytes, platelets, ESR;

***biochemical blood parameters:** total protein, creatinine, urea, AST, ALT, CK, total bilirubin, glucose, sodium, potassium, cholesterol, HDL-C, triglycerides;

***coagulogram:** fibrinogen, activated partial thromboplastin time (aPTT), INR, prothrombin;

***common urine analysis:** color, transparency, reaction, density, glucose, protein, bilirubin/urobilinogen, white blood cells, red blood cells.

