The individual identification code assigned to the patient is not subject to change.

The Investigator should maintain a separate Identification Registry containing the individual numbers, surnames, dates of birth, addresses, phone numbers, and medical records (if available). Only the initials, dates of birth, and unique patient numbers that are part of the Individual Patient Identification Code will be used in the report and trial documentation.

The randomization plan will be known by the Principal Investigator and Regulatory Authorities.

Visit 2.

- Administration of Fortelyzin® or Actilyse®.
- On Visit 2, the changes in neurological status will be recorded, as well as registration and evaluation of bleeding and adverse events based on patient complaints, data from neurological, physical, and laboratory-instrumental studies.

Table 7. Monitoring of parameters at the moment of thrombolysis

Trial parameter	Frequency of examination
BP	Every 15 minutes to 2 hours after the start of thrombolysis
Vital signs	Every 30 minutes for 6 hours
NIHSS	Every 15 minutes for 1 hour
Meningeal symptoms	Every 15 minutes for 1 hour

Table 8. Monitoring of parameters during the first day (24h) after thrombolysis

Trial parameter	Frequency of examination
BP	Every hour until the end of the day (within 24 hours)
Vital signs	Every 30 minutes to 6 hours, then every hour until the end of the day
Meningeal symptoms	Every hour for 24 hours
NIHSS	Every hour for 24 hours

- CT/MRI 24 hours after TLT or if the patient's condition worsens
- assessment of CT changes according to ASPECTS
- registration of adverse events (AE)
- assessment of bleeding

All adverse events identified should be recorded in the Case Report Form (CRF). The Investigator should report the adverse events to Roszdravnadzor within the next 24 hours. The assessment of bleeding is carried out according to the corresponding scales (see Safety assessment). Monitoring of coagulogram parameters (fibrinogen) will be carried out within 24 h from the time of Fortelyzin® or Actilyse®

administration. CT/MRI examination of the brain will be repeated 24 hours after the thrombolysis or if the patient's condition worsens.

During the visit, patients will receive treatment in accordance with the Russian Clinical Guidelines for Thrombolytic Therapy in Ischemic Stroke, 2015.

Visit 3.

- verification of the stroke subtype according to TOAST criteria
- measurement of vital signs
- physical examination

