- assessment of neurological status scales scores
- coagulogram
- complete blood count
- common urine analysis

Visit 4.

- measurement of vital signs
- physical examination
- assessment of neurological status scales scores
- CT/MRI scans
- assessment of CT changes according to ASPECTS
- ECG
- ultrasound examination of brain vessels (if necessary)
- coagulogram
- complete blood count
- biochemical analysis of blood
- common urine analysis.

Visit 5.

- measurement of vital signs
- physical examination
- assessment of neurological status scales scores

- ECG
- coagulogram
- complete blood count
- biochemical analysis of blood
- common urine analysis.

During visits 2-5, information about adverse events and bleeding will be collected and recorded into the Case Report Form. The data on adverse events will be shared with the Sponsor. In addition, information about changes in concomitant therapy will also be recorded.

Visit 6.

- measurement of vital signs
- collection of information about SAE and AE, as well as recording the Bartel index scores, Rankin and NIHSS scale scores
- collection of information about concomitant diseases.

Unscheduled visits

Unscheduled visits may be made at the discretion of the Investigator or at the initiative of the patient. For all unscheduled visits, the corresponding CRF page should be filled out.

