Manifestations of UAR regress after the drug discontinuation and occur again after repeated administration.

- **Probable.** Clinical manifestations of UAR, laboratory findings deviations are associated with the time of drug administration, unlikely to be related to concomitant diseases or other factors, and which regress with drug withdrawal. Response to the drug re-challenge is unknown.
- **Possible.** Clinical manifestations of UAR, laboratory findings deviations associated with the time of drug administration, but they can be explained by the presence of concomitant diseases or other drug administration and the influence of chemical compounds. Information on drug withdrawal response is unclear.
- **Questionable.** Clinical manifestations of UAR, changes in laboratory findings occur in the absence of a clear temporal association with the product administration; other factors are present (medicinal products, diseases, chemicals), which may be the cause of their occurrence.
- **Unlikely.** Clinical manifestations of UAR, laboratory findings deviations related to UAR, are difficult to assess. Additional data are needed for assessment, or the data are currently being analyzed.
- **Unclassified.** Reports on suspected UAR cannot be assessed, due to insufficient information, or it is contradictory.

In the case of adverse events, the choice of measures (follow-up, non-drug or drug therapy, hospitalization, and/or prolongation of existing hospitalization) is made by the physician-investigator based on the patient's interests to create optimal conditions and provide the patient with needed medical care.

Patients are monitored in the center until the full completion of any adverse event that occurred during the trial, and in the case of the development of a chronic disease - until the condition is stabilized. Adverse events in the form of changes in laboratory findings are observed until the normalization of the values or until the diagnosis of the chronic disease that caused such changes.

Serious adverse event (SAE)

A serious adverse event (SAE) is defined as any adverse event (AE) that at any dose results in:

- * death and/or disability;
- * development of a life-threatening condition;
- * prolongation of existing hospitalization;
- * development of congenital anomalies or malignant tumors.

In addition, any severe bleedings will be considered as SAEs in this trial:

- "major bleeding" according to the TIMI classification

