- "severe or life-threatening bleeding" according to the GUSTO classification
- symptomatic intracerebral hemorrhage (SICH) was defined as any hemorrhage with neurologic deterioration, as indicated by an NIHSS score for 4 points and more than its value at baseline or the lowest one at 7 days after thrombolysis or any hemorrhage leading to death and had been identified as a predominant cause of neurologic deterioration (definition ECASS III)

Adverse events that do not fall into these categories should not be regarded as serious.

Any SAE, regardless of the causal relationship with the drug under trial, must be reported to Roszdravnadzor no later than 24 hours after the Investigator became aware of the SAE.

All paragraphs in the appropriate SAE report form must be filled in. Information about the SAE should be included in the Case Report Form.

Bleedings

All bleeding events should be registered in the patient's CRF. Each bleeding is classified according to the GUSTO and TIMI scales. Bleeding that is classified according to TIMI as "major" or "severe or life-threatening" – according to the GUSTO scale are considered as SAE in this trial.

Safety assessment is carried out based on the number and severity of AEs and SAEs detected during the trial.

If a serious adverse event occurs, the Investigator must:

- provide (if necessary) appropriate qualified medical care, including laboratory and instrumental studies;
- inform Roszdravnadzor within 24 hours about the occurrence of SAE and send (fax, e-mail) a Report form on a serious adverse event;
- indicate all adverse events in the patient's CRF;
- continue to monitor the patient's condition until the SAE is fully completed.

In addition, if there is major or moderate bleeding, its localization is indicated:

- gastrointestinal tract;
- urogenital tract;
- retroperitoneal space;
- central nervous system;
- parenchymal organs.

In minor bleeding occurs, the immediate cause of its occurrence and/or localization is indicated:

- puncture;
- damage to blood vessels;
- bleeding from the gums.

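### The closed SAE list in Section 12 leaves out new hospital admission, and the only tolerability criterion is a one-arm zero-event rule in a comparative trial

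*Combined protocol and SAP*

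**What the plan says.** **Seriousness.** Section 12 (Serious adverse event) defines an SAE by four outcome lines: death or disability, a life-threatening condition, "prolongation of existing hospitalization", and congenital anomaly or malignant tumour. It adds severe bleeding: TIMI major, GUSTO severe or life-threatening, and symptomatic intracerebral haemorrhage by the ECASS III definition. It then states: "Adverse events that do not fall into these categories should not be regarded as serious". Earlier in the same section, the measures an investigator may take for an adverse event are given as "follow-up, non-drug or drug therapy, hospitalization, and/or prolongation of existing hospitalization".

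**Follow-up.** Section 8 keeps patients in hospital "before discharge (on average 14 days), with an outpatient visit on the 90th day". Table 5 schedules no visit between day 14 and day 90. Section 9, Visit 6, provides for "collection of information about SAE and AE, as well as recording the Bartel index scores".

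**Reporting.** Under Section 12 any SAE "must be reported to Roszdravnadzor no later than 24 hours after the Investigator became aware of the SAE". Section 9, within the Visit 2 text, says: "The Investigator should report the adverse events to Roszdravnadzor within the next 24 hours". Section 4.2 says that the approving institutions will be "informed about all adverse events associated or possibly related to the use of the study drug", with no deadline.

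**Tolerability.** The opening of Section 12 regards the drug as well tolerated if the trial registers no severe event, explained in brackets as fatal or life-threatening, that the investigator thinks may be linked to the drug studied. The grading scale in the same section defines severe differently, by inability to work or carry out daily activities. The safety objective in Section 6 is a comparison with Actilyse, and the design in Section 8 is open-label.

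**The concern.** The seriousness rule gives an arbitrary result. An event that lengthens the index stay is an SAE. An event after discharge that needs a new admission, and meets no other criterion, is not. Because the list is closed, the investigator has no discretion to call it serious.

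SAE status matters in three places. The number of SAEs is a listed safety criterion (Protocol Summary and Section 12). It triggers the 24-hour report in Section 12. Drug-related SAEs are the event class named in the first early-termination criterion of Section 7.5, although the second criterion there is broader.

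The tolerability sentence is a lesser matter. A statement made under it would turn on one event attributed by an unblinded investigator, and the Actilyse arm would have no bearing on it.

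**Working it through.** **Part 1: is new admission covered anywhere?** This is a reading of the text.

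1. None of the four outcome lines or the three bleeding categories is a new admission.
2. Prolongation cannot easily be read to include admission, because the adverse-event text of the same section names hospitalisation and prolongation as two separate measures.
3. The closing sentence excludes everything not listed.
4. A readmission that is fatal, disabling, life-threatening or due to a listed bleed stays serious. Only the remainder is affected.
5. The event is not lost: Visit 6 collects adverse events. It moves from the SAE count to the AE count.
6. The Section 9 reporting sentence sits under Visit 2, so it does not clearly reach events after discharge. If it covered every adverse event at every visit, the separate SAE deadline in Section 12 would be redundant. Section 4.2 covers related events only.

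Possible size per arm: the documents give no rate, so these are assumed shares of randomised patients with a readmission that meets no other criterion.

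| Assumed share | × 168 | × 152 (without the dropout allowance) |
|---|---|---|
| 2% | 3.4 | 3.0 |
| 5% | 8.4 | 7.6 |
| 10% | 16.8 | 15.2 |

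The period after average discharge is (90 − 14)/90 = 84% of follow-up time. That is a share of time, not of events.

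**Part 2: the zero-event criterion.**

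The arm size comes from Section 17 and reproduces. With 54.8% in both arms, a 16% margin, one-sided 0.025 (bilateral 5%) and 80% power:

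n = (1.960 + 0.842)² × 2 × 0.548 × 0.452 / 0.16² ≈ 152 per arm, and 152 × 1.10 = 167.2, rounded up to 168.

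The point does not dispute this figure; it only supplies n.

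If r is the true rate of qualifying events on Fortelyzin, P(at least one in 168) = 1 − (1 − r)^168.

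| True rate r | Source | P(at least one), i.e. criterion failed |
|---|---|---|
| 0.1% | assumed | 15% |
| 0.46% (7/1531) | Section 2, haemorrhagic stroke in infarction patients | 54% |
| 1% | assumed | 82% |
| 2% | assumed | 97% |

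The exact 95% interval for 7/1531 is 0.18% to 0.94%, which gives 27% to 80%. This range reflects sampling error only. The rate is an illustration: Section 2 gives a 15 mg dose in infarction against 10 mg in stroke, and reports concomitant anticoagulant and dual antithrombotic therapy in the infarction patients. Using it also assumes that every such event is life-threatening and attributed to the drug.

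- Rate for an 80% chance of meeting the criterion: 1 − 0.8^(1/168) = 0.13%, about 1 in 750.
- Upper limit after 0/168, two-sided exact 95%: 1 − 0.025^(1/168) = 2.2%. The one-sided 95% bound is 1 − 0.05^(1/168) = 1.8%.

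So one event fails the criterion at modest rates, and meeting it still does not exclude a rate of about 2%. The Actilyse rate enters none of these expressions.

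**The case against.** **On the SAE list.** The same definition applies to both arms. The readmission is still documented as an adverse event with severity, causality, action and outcome, and is counted among adverse events. Related events go to the approving bodies, and the Visit 2 text can be read as a general 24-hour rule. No primary endpoint changes, nor do mortality or haemorrhagic transformation, and the link to early termination is remote. Only a residual of readmissions is affected, and its size is pure assumption. Using 168 also includes the dropout allowance, and patients who die before discharge cannot be readmitted, so the counts are towards the upper end at each assumed rate. All of this limits the size of the problem. It does not restore admission as a criterion, and the SAE count and SAE report are still defined by a list that excludes it.

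**On tolerability.** The sentence feeds no test or stopping rule. The listed safety endpoints and the general between-group tests in Section 18 stand beside it. The double use of severe may be a translation effect, and the bracket makes the sentence usable as written. The 0.46% comes from another population, so its probabilities are illustrative only. These points stand, and they are why this part is secondary. The sentence is nevertheless the only tolerability criterion stated for this trial, and it is not comparative.

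**Conclusion.** Both parts hold, and the text should be corrected. Followed exactly, Section 12 classes a post-discharge readmission that meets no other criterion as non-serious and leaves it out of the SAE count and the 24-hour SAE report. No other section clearly closes the gap. This rests on the wording alone. The number of patients affected cannot be derived from the documents; roughly 3 to 17 per arm corresponds to assumed shares of 2% to 10%.

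The tolerability criterion is a one-arm, zero-event rule based on open-label attribution, although the safety objective is comparative. Its failure probabilities depend on assumed event rates, since the documents give none for Fortelyzin in stroke. It does not remove or replace the planned safety comparisons.

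**What to change.** 1. In the SAE list of Section 12, change the hospitalisation item to *requires hospital admission or prolongs existing hospitalisation*.
2. Reconcile the reporting sentences in Section 9 (Visit 2) and Section 12, so that together they state which events need a 24-hour report and through which visit.
3. Delete the zero-event tolerability sentence. Base the tolerability statement on between-arm risk differences with 95% confidence intervals for day-90 all-cause death, ECASS III symptomatic haemorrhagic transformation and SAEs, regardless of attribution.

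The cost is one list item, one reconciled reporting rule and one deleted sentence, plus some extra SAE forms for readmissions. The endpoint data are already planned; only the risk-difference intervals are new analysis. No further data, visits or patients are needed.

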13. CASE REPORT FORM

Primary data means all the information contained in the original medical records and their certified copies, describing the results of clinical observations, examinations, and other activities, allowing to restage the trial and assess it. Primary data is included in the primary documentation (originals or certified copies thereof).

Data entered in the CRF will be confirmed by other primary documents.

For the tests performed in the central laboratory, it is necessary to attach a copy of the analysis results to the CRF.

All information obtained during the trial about the patient's condition, data from laboratory and instrumental studies, and adverse events are recorded in the CRF.

Erroneous records are crossed out with a single line so that it can be read. Correct records are made nearby. All records and corrections are dated and signed by the physician-investigator.

The original documents should be available for periodic review. The original CRFs are transferred to the Sponsor upon completion of the trial.

14. DRUG STORAGE AND ACCOUNTING

The study drug will be properly labelled. The label will indicate the name and dose of the drug, expiration date, storage conditions. The drug package will have an inscription: "For clinical trial use only". It is unacceptable to use the drug in patients not included in this trial.

The drug is delivered to a research center on demand and stored in a dry place at a temperature of 2-25 °C. Only Investigators have access to the drug. The packaging of the used drug must be preserved and returned to the Sponsor.

The Regulatory Authorities will require accounting for all the necessary drugs received by each research center. The following information should be entered into the register: the date of issue, date of administration, dose, and patient to whom the drug was administered. When using each dose of the drug, the corresponding record is made in the patient's medical history and in the patient's CRF (date and time, batch number of the drug, and the initials of the person who prepared the drug for administration).

The patient's number, date, and time of administration should also be indicated on the drug package.

Drug accounting will be controlled by the Monitor during visits to the research center.

At the end or termination of the trial, the form for accounting the trial product should be completed and verified; all discrepancies should be clarified, and their cause should be indicated in the documentation. According to the requirements of the Regulatory Authorities, all unused research materials must be returned to the Sponsor at the end of the trial. It is allowed to dispose of empty vials in the research center, but only after the use of the drug has been checked by the Monitor.

